#### **10.11. Study Completion**

Each subject received atherectomy by Jetstream system will be followed for 12 months after the index procedure. For primary endpoint evaluation, the data of each such subject must be collected until the 12-month follow-up.

#### **10.12. Source Documents**

Where copies of the original source document as well as printouts of original electronic source documents are retained, these shall be signed and dated by a member of the investigation center team with a statement that it is a true reproduction of the original source document.

### **11. Statistical Considerations**

The sample size justification and the power analysis described here are associated with the primary hypotheses. Roll-in subjects will be analyzed separately for observational purpose. The details of all statistical analyses will be described in the Statistical Analysis Plan.

#### **11.1. Primary Endpoints**

The overall sample size is consist of the primary cohort and roll-in subjects. The sample size of the primary cohort is justified by hypothesis parameters and driven by the primary safety 30-day endpoint to preserve adequate statistical testing power for both primary effectiveness and safety endpoints.

### 11.1.1. Primary Safety Endpoint

The primary safety endpoint is the rate of major adverse event (MAE), defined as all-cause death, target limb unplanned major amputation and/or target lesion revascularization (TLR), within 30 days post index procedure.

#### 11.1.1.1. Safety Hypotheses

The primary safety hypothesis to be tested is that 30-day MAE-free rate in subjects treated with Jetstream System exceeds a PG of 88% at one-sided significance level of 2.5%.

The null hypothesis ( $H_0$ ) states that the PG is not met as opposed to the alternative hypothesis ( $H_1$ ) which states that the PG is met. The hypotheses inequalities are shown below:

$$H_0: Pt \leq PG \text{ (not met)}$$

$$H_1: Pt > PG \text{ (met)}$$

where  $Pt$  is the 30-day MAE-free rate for the subjects treated with Jetstream System and the PG is 88%.

The PG of 88% was estimated on the basis of available literature and is consistent with those described atherectomy outcomes.

#### 11.1.1.2. Safety Sample Size

The overall sample size is consist of the primary cohort and roll-in subjects. The primary cohort is driven by the primary safety endpoint.

- Power  $\geq 90\%$
- One-sided overall significance level = 2.5% (alpha)
- PG for 30-day MAE-free rate = 88%
- Expected 30-day MAE-free rate = 99%
- Attrition rate = 15% (loss to follow-up at 30 days)
- A minimum of 50 subjects to be evaluable at 30 days that will provide at least 99% power for the primary safety endpoint
- A sample size of 60 subjects to be enrolled in the primary cohort at baseline

With additional 2 roll-in subjects per site, the overall subjects to be enrolled are approximately 80.

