### 11.2. *Success Criteria*

#### Success Criteria for Primary Safety Endpoint

Jetstream System will be concluded as meeting PG for device safety if the one-sided lower 97.5% confidence bound on the observed 30-day MAE-free rate is greater than 88%.

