Sample Size Parameters	The overall sample size is consist of the primary cohort and roll-in subjects. The sample size of primary cohort is driven by the primary safety endpoint.

**Prospective, non-randomized, multicenter clinical study of the JETSTREAM™
Atherectomy System (Jetstream) in treatment of occlusive atherosclerotic lesions in the
superficial femoral and/ or proximal popliteal arteries in Chinese patients
(JETSTREAM CHINA)**

	
• Power $\geq 90\%$• One-sided overall significance level = 2.5% (alpha)• PG for 30-day MAE-free rate = 88%• Expected 30-day MAE-free rate = 99%• Attrition rate = 15% (loss to follow-up at 30 days)• A minimum of 50 subjects to be evaluable at 30 days that will provide at least 99% power for the primary Safety endpoint• A sample size of 60 subjects to be enrolled in the primary cohort at baseline• With additional 2 roll-in subjects per site, the overall subjects to be enrolled are up to 72.
Core Lab	All angiographic and DUS readings will be assessed by independent core laboratories
Study Committee	A clinical event committee (CEC) will review and adjudication following pre-specified CEC events: 
• Death• Target limb major amputation• Target vessel revascularization (TVR) and target lesion revascularization (TLR)• Distal embolization requiring additional treatment• Perforation during index procedure that requires additional treatment

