3.1.3 Safety Sample Size

The overall sample size is consist of the primary cohort and roll-in subjects. The primary cohort is driven by the primary safety endpoint. Approximately 72 subjects are planned to be enrolled in the single-arm study. The sample size justification is based on the following assumptions.

- Power $\geq 90\%$
- One-sided significance level (alpha) = 2.5%
- PG for 30-day MAE-free rate = 88%
- Expected 30-day MAE-free rate = 99%
- Attrition rate in 30 days = 15%
- N = 50 evaluable subjects are required at 30 days
- A maximum of N = 60 subjects to be enrolled in the primary cohort at baseline
- With additional 2 roll-in subjects per site, the overall subjects to be enrolled are approximately 72.

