3.1.4 Safety Statistical Methods

A normal approximation test for comparing observed 30-day MAE-free rate with the PG will be used to assess the safety hypotheses for a minimum of 50 evaluable subjects.

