3.1.5 Worst Case Assessment for Safety

The PG of 88% will only allow 1 subjects with 30-day MAE out of 50 subjects treated with Jetstream. That is, the observed 30-day MAE-free rate in Jetstream will need to be at least 98% (49/50) in order to claim safety PG.

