7.3 SAS Codes for Chi-Square Test

The confidence intervals and the p-value for the chi-square test can be produced by the following SAS code.

```
proc freq data=;
  tables xx/binomial(p=) alpha=;
  run;
```

For example, the worst case scenario in the PG testing of the primary safety hypotheses is used for the exercise. A dummy frequency table is coded as below.

```
%let total=50; %let yes=49; %let no=&total.-&yes.;

data dsn1;
  yn=1; wgt=&yes.; output;
  yn=0; wgt=&no.; output;
run;
```

A list of SAS codes for Binomial and Chi-Square method is used for PG=88% and 95% confidence limits.

```
proc freq data=dsn1 order=data;
  tables yn/ binomial(p=0.88) alpha=.05;
  weight wgt;
run;
```

The SAS output for the worst case scenario is presented below.

Binomial Proportion	
yn = 1	
Proportion	0.9800
ASE	0.0198
95% Lower Conf Limit	0.9412
95% Upper Conf Limit	1.0000
Exact Conf Limits	
95% Lower Conf Limit	0.8935
95% Upper Conf Limit	0.9995
Test of H0: Proportion = 0.88	
ASE under H0	0.0460
Z	2.1760
One-sided Pr > Z	0.0148
Two-sided Pr > Z	0.0296
Sample Size = 50	

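### The stated power of 99% or more for primary safety with 50 evaluable subjects is about 91% under the plan's own rule of at most 1 MAE in 50

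*Protocol*

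**What the plan says.** Protocol 11.1.1.2 lists the safety design inputs: performance goal 88%, expected 30-day MAE-free rate 99%, one-sided alpha 2.5%, target power of at least 90%, 15% attrition and 60 subjects enrolled in the primary cohort. The same list then states: "A minimum of 50 subjects to be evaluable at 30 days that will provide at least 99% power for the primary safety endpoint". The Protocol Synopsis and the SAP Synopsis carry the same statement. SAP 3.1.3 gives the 90% target and "N = 50 evaluable subjects are required at 30 days", without the 99%.

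Three SAP sections fix the decision rule:

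- 3.1.4 names the test: "A normal approximation test for comparing observed 30-day MAE-free rate with the PG will be used to assess the safety hypotheses".
- 3.1.5 gives the consequence at 50 subjects: "The PG of 88% will only allow 1 subjects with 30-day MAE out of 50 subjects treated with Jetstream". It restates this as at least 49/50, or 98%.
- 7.3 works that case in SAS, saying that "the worst case scenario in the PG testing of the primary safety hypotheses is used for the exercise". For 49/50 it prints a standard error under the null of 0.0460, Z = 2.1760 and one-sided p = 0.0148.

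The success criterion in Protocol 11.2 and SAP 3.3.1 is that "the one-sided lower 97.5% confidence bound on the observed 30-day MAE-free rate is greater than 88"%. Neither section names the type of bound.

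**The concern.** Once the number of subjects, the number of events allowed and the assumed event rate are all stated, power is a binomial probability with nothing left to choose. A rule that tolerates only one event in 50 is strict: at a 1% event rate, two or more events in 50 are not rare. A claim of 99% or more therefore looked too high.

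The figure matters because the safety endpoint sets the size of the primary cohort and the study cannot succeed without it. Under SAP 3.3, effectiveness is tested only if safety is met. A reader who takes the sentence at face value would put the risk of failing on safety with a device that performs as assumed at 1% or less.

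**Working it through.** **Inputs.** Null MAE-free rate p0 = 0.88, expected rate p1 = 0.99, one-sided alpha 0.025 and n = 50 (Protocol 11.1.1.2). The test uses the null variance (SAP 7.3).

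**Step 1: reproduce the plan's decision rule.** Z = (x/n − p0) / √(p0(1 − p0)/n), with √(0.88 × 0.12/50) = 0.04596.

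- 49/50: (0.98 − 0.88)/0.04596 = 2.176, one-sided p = 0.0148. This matches SAP 7.3 and passes.
- 48/50: (0.96 − 0.88)/0.04596 = 1.741, one-sided p = 0.041. This fails at 0.025.

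The limit of one MAE in SAP 3.1.5 is therefore what the named test gives.

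**Step 2: exact power of that rule.** With a 1% event rate:

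P(0 events) + P(1 event) = 0.99^50 + 50 × 0.01 × 0.99^49 = 0.6050 + 0.3056 = 0.9106.

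**Step 3: power by the normal-approximation formula for the same test.**

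Φ[(0.11 − 1.96 × √(0.88 × 0.12/50)) / √(0.99 × 0.01/50)] = Φ[(0.11 − 0.0901)/0.01407] = Φ(1.416) = 0.922.

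Neither calculation gives 99%.

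**Step 4: what 99% would require at n = 50.**

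| MAEs allowed in 50 | Exact power at 99% MAE-free | Exact type I error at 88% |
|---|---|---|
| 0 | 60.5% | 0.2% |
| 1 (the plan's rule) | 91.1% | 1.3% |
| 2 | 98.6% | 5.1% |
| 3 | 99.8% | 13.5% |

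Power of 99% at 50 subjects needs three MAEs to be allowed, with a type I error far above 2.5%.

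**Step 5: other evaluable counts, same Z-test.**

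| Evaluable | MAEs allowed | Exact power | Exact type I error |
|---|---|---|---|
| 50 | 1 | 91.1% | 1.3% |
| 51 (60 × 0.85) | 1 | 90.8% | 1.2% |
| 54 | 1 | 89.8% | 0.8% |
| 56 | 1 | 89.2% | 0.7% |
| 57 | 2 | 98.0% | 2.6% |
| 60 | 2 | 97.8% | 2.0% |

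The allowed count stays at one through n = 56, so power drifts down from 50 to 56, falls just under 90% at 54 to 56, and then jumps at 57.

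**Step 6: could the confidence bound explain the 99%?** Lower 97.5% limits:

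| Result | Wald | Wilson | Clopper-Pearson |
|---|---|---|---|
| 49/50 | 94.1% | 89.5% | 89.4% |
| 48/50 | 90.6% | 86.5% | 86.3% |

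Wilson and Clopper-Pearson agree with the Z-test at n = 50. The Wald limit would pass 48/50, which SAP 3.1.5 rules out. Even then power at 50 is 98.6%, still under 99%, with a type I error of 5.1%.

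**The case against.** The strongest objection is that little turns on the sentence. The planning target is at least 90%, 50 evaluable subjects meet it, and SAP 3.1.3 gives only that target. No analysis or decision uses the 99%. This stands, and it is why the point is a correction and not a design failure.

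A second objection is that the rule is less settled than it seems, because the success criterion is a bound of unnamed type and SAP 7.3 prints the Wald limit (0.9412) ahead of the exact one (0.8935). With a Wald rule the gap at n = 50 shrinks to 0.4 points, and with all 60 evaluable (three MAEs allowed) power would be 99.7%. But the plan's sentence is about 50 subjects, where the Wald rule still falls short. That rule also contradicts SAP 3.1.5 and has an exact type I error of 5.1% at 50 and 6.0% at 60. The ambiguity is real but does not rescue the figure.

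A third objection is that quoting power only at 50 and 60 suggests a steady rise between them. This is fair, given the dip at 54 to 56, and the corrected wording should say so.

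**Conclusion.** The concern holds. With 50 evaluable subjects and the plan's rule of at most one MAE, power is 91.1% exact (92.2% by normal approximation), about 8 percentage points below the stated figure. The chance that a device performing as assumed misses the safety goal is about 9% at 50 evaluable and about 2% if all 60 are evaluable.

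This rests on the plan's own 99% MAE-free assumption, on independent subjects with the same event probability, and on the rule in SAP 3.1.5 and 7.3. The documents do not show how the 99% was obtained. The normal-approximation formula gives 99.3% at one-sided alpha 0.05, and a version using only the variance at 99% gives nearly 100%, so the origin cannot be inferred. The separate 99% power statement for effectiveness is not affected.

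**What to change.** In the Protocol Synopsis, Protocol 11.1.1.2 and the SAP Synopsis, replace the 99% claim with wording to this effect: *assuming a 99% MAE-free rate, power is about 91% with 50 evaluable subjects (at most 1 MAE) and about 98% if all 60 are evaluable (at most 2 MAEs); between these counts it does not rise steadily and is lowest, about 89%, at 56.*

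As a secondary clarification, Protocol 11.2 and SAP 3.3.1 should name the bound and state that it gives the same decision as SAP 3.1.5 and the SAP 7.3 test. That excludes the Wald bound. The Wilson bound matches the Z-test at every evaluable count from 48 to 60. Clopper-Pearson differs only at 57, where it allows one MAE (power 88.9%) while the Z-test and Wilson allow two (exact type I error 2.63%, slightly above 2.5%). The sponsor can choose either with that difference in view.

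The cost is wording in three places and an optional clause in two more. The sample size, alpha, performance goal and 1-in-50 rule do not change. The stated power becomes less favourable but still meets the 90% target at 50 evaluable.

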#### 11.1.1.3. Safety Statistical Test Method

A normal approximation test (e.g. Chi-Square Test) will be used to assess the one-sided hypothesis of PG.

### 11.1.2. Primary Effectiveness Endpoint

The primary effectiveness endpoint is the acute reduction of percent diameter stenosis (%DS) post atherectomy but prior to any adjunctive therapy, when compared to its baseline diameter stenosis (absolute mean percentage).

#### 11.1.2.1. Effectiveness Hypotheses

The primary effectiveness hypothesis to be tested is that acute reduction of percent diameter stenosis (%DS) in subjects treated with Jetstream System exceeds 40%\* within subject at one-sided significance level of 2.5%.

\*The expected mean acute reduction (i.e. %DSbefore Jetstream – %DSafter Jetstream) was 40%; the primary effectiveness hypothesis is to demonstrate there is a significant acute reduction (>0). See Statistical Analysis Plan for detail.

The null hypothesis ( $H_0$ ) states that there is no treatment effect before and after subjects treated with Jetstream System as opposed to the alternative hypothesis ( $H_1$ ) states that there is a treatment effect. The hypotheses inequalities are shown below:

$$H_0: \Delta t \leq 0 \text{ (not met)}$$

$$H_1: \Delta t > 0 \text{ (met)}$$

where  $\Delta t$  is the averaged difference in acute reduction of %DS before and after the subjects treated with Jetstream System and the within-subject treatment effect is 40% with standard deviation of 18% derived by the Pathway PVD study, Jetstream Calcium study and JET Registry\*\*.

\*\*The before-and-after atherectomy in the Pathway PVD shows  $79.4\% \pm 17.7\%$  and  $35.0\% \pm 16.1\%$  respectively. The before-and-after atherectomy in Jetstream Calcium study shows  $86.9\% \pm 9.0\%$  and  $37.0\% \pm 13.0\%$ . The before-and-after atherectomy in JET Registry shows  $91.1\% \pm 9.8\%$  and  $44.4\% \pm 20\%$ , and the acute reduction of %DS is  $46.7\% \pm 20.5\%$ .

#### 11.1.2.2. Effectiveness Sample Size/Power Analysis

The power analysis for the primary effectiveness endpoint is based on the following assumptions.

- One-sided significance level (alpha) = 2.5%
- Expected acute reduction of percent diameter = 40% with the common standard deviation estimated to be within the range of historical data

The sample size is driven by the primary safety endpoint to provide at least 99% power to assess the primary effectiveness endpoint.

#### 11.1.2.3. Effectiveness Statistical Method

A paired t-test will be used to assess the one-sided hypothesis of reduction in %DS before and after subjects treated with Jetstream System.

### 11.2. *Success Criteria*

#### Success Criteria for Primary Safety Endpoint

Jetstream System will be concluded as meeting PG for device safety if the one-sided lower 97.5% confidence bound on the observed 30-day MAE-free rate is greater than 88%.

#### Success Criteria for Primary Effectiveness Endpoint

Jetstream System will be concluded as meeting endpoint for device effectiveness if the one-sided lower 97.5% confidence bound on the difference between before and after atherectomy in %DS within subject is greater than zero.

#### Success Criteria for the Study

If the primary safety and the primary effectiveness endpoints are both met, the study will be considered a success and both device safety and effectiveness will be claimed.

### **11.3. General Statistical Methods**

#### **11.3.1. Analysis Sets**

The primary and pre-specified additional endpoints will be analyzed on an ITT basis and on a pre-protocol basis. For the ITT analysis, all subjects who sign the written ICF and are enrolled in the study will be included in the analysis sample, regardless of whether the subject used the Jetstream System. For the pre-protocol analysis, only enrolled subjects who are treated with the study device in the target lesion will be included in the analysis sample.

Roll-in subjects will be analyzed separately for observational purpose.

#### **11.3.2. Control of Systematic Error/Bias**

Selection of subjects will be made from the investigators' general or professional referral population. All subjects meeting the inclusion/exclusion criteria that have signed the protocol-specific ICF will be eligible for enrollment in the trial. Consecutively eligible subjects should be enrolled into the study to minimize selection bias. In determining subject eligibility for the study, the investigator's assessment of imaging will be used. The effectiveness endpoint data obtained from the core laboratory and the safety adjudicated data from independent Clinical Event Committee (CEC) will be used for the primary analyses.

#### **11.3.3. Number of Subjects per Investigative Site**

No study sites will be allowed to enroll more than 35% (N=28) of the total number of enrolled subjects to avoid treatment center bias and ensure homogeneous study results.

#### **11.3.4. Baseline Data Analyses**

Subject demographics, and clinical characteristics, site-reported and core lab reported lesion characteristics, procedure assessment, device information, and medication compliance will be summarized using descriptive statistics. The analysis level may be (but will not be limited to) by subject, lesion, procedure, or device.

For continuous and/or ordinal variables, the descriptive statistics will include mean, standard deviation, number evaluated, minimum and maximum. Some specific variables may also include additional statistics such as median and confidence intervals. For binary or categorical variables, the descriptive statistics will include percentage, numerator, denominator, and number evaluated. Some variables may include confidence intervals as needed.

### **11.3.5. Secondary Endpoint Assessments**

Secondary assessments may refer to (but not limited to) peri-procedural complications, clinical/procedural/hemodynamic success, safety/effectiveness endpoints, any type of AE rates at time points that data is collected (details refer to **Section 6.2.2.**). All additional assessments are observational.

### **11.3.6. Interim Analyses**

Steering Committee can make the decision to conduct the interim analyses accordingly (such as the process seriously delayed due to epidemic).

### **11.3.7. Subgroup Analyses**

Primary endpoints and/or additional assessments will be summarized by the following categories (but not limit to):

- Lesion location (distal, mid, proximal, ostial )
- Sex (male, female)
- Age (-64, 65-74, 75-)
- Lesion Characteristics (lesion length -50, 50-100, 100-150, 150- mm)
- Jetstream Catheter size (SC1.6, SC1.85, XC 2.1/3.0, XC 2.4/3.4)
- Diabetes (medically treated, non-medically treated)

All subgroup analyses are observational.

### **11.3.8. Sensitivity Analysis**

Sensitivity analyses for the primary effectiveness and/or safety endpoints assessment will be conducted to assess the impact of missing data on the result's robustness.

### **11.3.9. Analysis Software**

All statistical analyses will be performed using the Statistical Analysis Software (SAS), version 9.2 or later (Copyright © 2002-2010 by SAS Institute Inc., Cary, North Carolina 27513, USA. All rights reserved).

### 11.3.10. Changes to Planned Analyses

Any changes to the planned statistical analyses made prior to performing the primary endpoint analysis will be documented in an amended Statistical Analysis Plan approved prior to performing the analysis. Changes from the planned statistical methods after performing the analysis will be documented in the clinical study report along with a reason for the deviation.

## 12. Data Management

### 12.1. *Data Collection, Processing, and Review*

Subject data will be recorded in a limited access secure electronic data capture (EDC) system.

The clinical database will reside on a production server hosted by EDC System. All changes made to the clinical data will be captured in an electronic audit trail and available for review by Boston Scientific Corporation (BSC) or its representative. The associated RAVE software and database have been designed to meet regulatory compliance for deployment as part of a validated system compliant with laws and regulations applicable to the conduct of clinical studies pertaining to the use of electronic records and signatures. Database backups are performed regularly.

The Investigator provides his/her electronic signature on the appropriate electronic case report forms (eCRFs) in compliance with local regulations. A written signature on printouts of the eCRFs must also be provided if required by local regulation. Changes to data previously submitted to the sponsor require a new electronic signature by the Investigator acknowledging and approving the changes.

Visual and/or electronic data review will be performed to identify possible data discrepancies. Manual and/or automatic queries will be created in the EDC system and will be issued to the site for appropriate response. Site staff will be responsible for resolving all queries in the database.

### 12.2. *Data Retention*

The Principal Investigator or Investigational site will maintain, at the investigative site, in original format all essential study documents and source documentation that support the data collected on the study subjects in compliance with ICH/GCP guidelines. Documents must be retained for 10 years after the formal discontinuation of the clinical investigation of the product. These documents will be retained by BSC until the product/device is no longer in use in compliance with local regulations. The Principal Investigator or his/her designee will take measures to ensure that these essential documents are not accidentally damaged or destroyed. If for any reason the Principal Investigator or his/her designee withdraws responsibility for maintaining these essential documents, custody must be transferred to an individual who will assume responsibility and BSC must receive written notification of this custodial change. Sites are required to inform Boston Scientific in writing where paper or electronic files are maintained in case files are stored off site and are not readily available.

